Given this train of evidence, we are proposing a small, exploratory clinical trial investigating the role of VC in PSC. The trial will be conducted by investigators with long careers dedicated to the study of PSC and other hepatobiliary disorders. The trial will be executed at two sites that are both tertiary referral centers for PSC.

I. Goal:

The overall goal of this study is to examine the safety, tolerability, and efficacy of daily dosing with vidofludimus calcium over a 6-month period on the clinical course and progression of primary sclerosing cholangitis.

The results will help us:

- Establish proof-of-concept that VC may show activity for the treatment of PSC
- Gain insight into the effect of VC on profiles of the proinflammatory cytokines IL-17 and IFN γ
- Establish data to design more comprehensive clinical studies

II. Impact of Study:

This open-label, single-arm pilot study will give us the opportunity to explore the potential of this novel drug to show activity in patients suffering from PSC, a rare but devastating disease with no known effective treatment.

III. Expected Outcome:

We hypothesize that in PSC, daily treatment with vidofludimus calcium will result in reduction of serum ALP, a surrogate marker that has been shown to strongly correlate with positive outcomes in PSC. Further, we hypothesize that treatment will result in a decrease in certain proinflammatory cytokines, particularly IL-17 and IFN γ . We expect based on a wealth of preclinical and clinical evidence that treatment with vidofludimus calcium will be safe and well tolerated.

IV. Specific Aims of the Study:

1. Determine if VC reduces serum alkaline phosphatase (ALP) in adults with PSC. Levels of serum ALP after 3 and 6 months of VC treatment will be compared with baseline (month 0).
2. Assess other liver biochemistries (an indication of general liver health) at 3 and 6 months of VC treatment and compare to baseline (month 0).
3. Determine if changes in the proinflammatory cytokines IL-17 and IFN γ predict

response to VC. Cytokines will be measured at baseline, 4 weeks, and 6 months.

If successful, this low-risk, high-reward study will lay the groundwork for larger, more comprehensive clinical studies investigating the efficacy of VC in PSC. This could ultimately lead to the development of a successful therapy for PSC and significantly improve patient outcome and quality of life.

RESEARCH STRATEGY

Significance

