Vidofludimus is a **potent inhibitor of human DHODH**, three times more effective than teriflunomide. A second important and distinguishing property of vidofludimus is its **potent inhibition of IL-17 and IFN γ release** from stimulated immune cells. Inhibition of IL-17 production was found to be independent of its effects on lymphocyte proliferation and it is believed that both these independent activities of vidofludimus contribute to its therapeutic effects in IBD.^{50,58} This **dual mechanism of action** confers a unique advantage over other DHODH inhibitors and makes vidofludimus a promising therapeutic option for both UC and PSC, diseases with frequent comorbidity and a common pattern of Th17 lymphocytic infiltration. With good clinical data for UC already in hand and a more comprehensive UC study in the works, a pilot trial for PSC is warranted. Success would result in a major step towards an effective

treatment for PSC where one does not currently exist.

Approach

We are proposing to test the hypothesis that vidofludimus calcium, a novel drug product, will be an effective treatment strategy for the rare but devastating disease primary sclerosing cholangitis. The rationale for this is based on **i) the strong linkage between ulcerative colitis and PSC; ii) the known involvement of Th17 lymphocytes and IL-17 in both disorders; iii) the demonstrated effect of vidofludimus on lymphocyte proliferation and IL-17 production; and iv) clinical evidence for the efficacy of vidofludimus in patients with UC.** Our approach is to investigate this hypothesis using a small two- center pilot study employing serum alkaline phosphatase, a surrogate marker having a well-established association with clinical outcome, as our primary endpoint. We further hypothesize that treatment with VC will affect profiles of proinflammatory cytokines and will assess IL-17 and IFNy levels as a potential early indicator of improvements in ALP.

The Specific Aims of the study are:

1. Determine if VC reduces serum alkaline phosphatase (ALP) in adults with PSC. Levels of serum ALP after 3 and 6 months of VC treatment will be compared with baseline (month 0).
2. Assess other liver biochemistries (an indication of general liver health) at 3 and 6 months of VC treatment and compare to baseline (month 0).
3. Determine if changes in the proinflammatory cytokines IL-17 and IFNy predict response to VC. Cytokines will be measured at baseline, 4 weeks, and 6months.

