 - c. Proinflammatory cytokine profile (IL-17 and IFN γ) [baseline, 4 weeks, and 6 months]

The most extensively studied surrogate endpoint in PSC is serum alkaline phosphatase (ALP). Our group at Mayo Clinic and others have reported an association between serum ALP and clinical outcomes in PSC. Specifically, normalization of serum ALP appears to be associated with long-term survival free of CCA, liver transplantation, liver-related death, and colorectal cancer and persistent ALP elevation has been associated with worse outcomes in PSC.⁵⁹⁻⁶¹ Therefore, we have chosen this simple, rapid, inexpensive, and minimally invasive test as our primary endpoint. AST, ALT, and bilirubin will be monitored to assess general liver health during the treatment. AST, ALT, or total bilirubin elevation can signal increased liver damage or liver cell necrosis, while elevated direct bilirubin may indicate bile duct obstruction. Further, it is hypothesized that treatment with VC will result in a reduction of IL-17 and IFN γ production. Levels of these cytokines will be measured at 4 weeks and at 6 months (end of study) and compared to baseline. The early 4-week time point will be used to determine whether early changes in these cytokines may predict improvements in ALP.

A 25% improvement in ALP with no more than a 33% worsening of AST after 6 months of treatment will be assessed as a positive outcome. While full normalization of ALP levels is unlikely over the short course of this pilot study, a 25% improvement would be deemed significant, indicating that VC has a positive effect on the progression of PSC. A less than 33% increase in AST levels concomitant with this ALP reduction would be acceptable, as it would be considered only a mild elevation. While a recent consensus statement from the International PSC Study Group indicates that transient elastography (TE), a new technique that allows non- invasive assessment of liver fibrosis, is one of the top three most promising surrogate endpoints for PSC (along with ALP and liver histology),⁶² it is unlikely that significant changes in TE would manifest in the 6-month course of this study. Thus, TE will not be included as an endpoint. Reduction of proinflammatory cytokines IL- 17 and IFN γ at the early 4-week time point concomitant with reduced ALP at the end of study would indicate a role for cytokine levels as an early predictor of improvements.

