A dosage of 30 mg vidofludimus calcium has been chosen based on data from previous clinical trials. Vidofludimus has been investigated in two Phase 1 trials. A single dose study (escalating 17.5 - 350 mg) and a multiple dose study (35 and 70 mg once daily over 14 consecutive days) were performed in nearly 90 healthy male volunteers. In these studies, vidofludimus demonstrated robust pharmacokinetics with a t_{max} at 4 hours, a half-life of about 36 hours, and a reasonable dose linearity, which justifies once daily dosing. At a dose of 35 mg vidofludimus, plasma trough levels between 4.4 and 5.8 μ g/ml were achieved, so that throughout the dosing interval plasma levels of vidofludimus were constantly above the IC_{50} values for inhibitory effects on stimulated human peripheral blood lymphocytes in vitro and for DHODH inhibition. In a Phase 2a study, vidofludimus (35 mg) demonstrated efficacy in patients with Crohn's disease and ulcerative colitis, with 88.5% of subjects responding to treatment.

Serum alkaline phosphatase (ALP) is one of the most extensively studied surrogate endpoint in PSC. Our group at Mayo Clinic and others have reported an association between serum ALP and clinical outcomes in PSC. Normalization of serum ALP appears to be associated with long-term survival free of cholangiocarcinoma, liver transplantation, liver-related death, and colorectal cancer, whereas persistent ALP elevation has been associated with worse outcomes in PSC. Therefore, we have chosen this simple, rapid, inexpensive, and minimally invasive test as the primary endpoint. Aspartate transaminase (AST), alanine transaminase (ALT), and bilirubin will be monitored to assess general liver health during the treatment. AST, ALT, or total bilirubin elevation can signal increased liver damage or liver cell necrosis, while elevated direct bilirubin may indicate bile duct obstruction. Part of the hypothesis being tested is that treatment with VC will result in a reduction of IL-17 and IFN γ production. Levels of these cytokines will be measured at 4 weeks and at 6 months and compared to baseline to determine whether early changes in these proinflammatory cytokines may predict improvements in ALP.

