- Elevated total bilirubin $\geq 2 \times$ baseline that does not return to within 10% of baseline within two weeks
- Serious allergic reaction
- Pregnancy or breastfeeding

Non-adherence to the study protocol by a study subject may, at the discretion of the principal investigator, be grounds for termination.

Statistical Analysis Plan: The proportion of patients with normalization of serum ALP at 3 months and 6 months and their corresponding confidence intervals will be estimated using exact binomial method. The primary endpoint is ALP normalization (within the normal limits of the laboratory test) rate at 6 months. We will define success as a 95% CI that does not overlap 0 at 6 months. Further, we will further investigate if the absolute ALP decreases over time using mixed model with repeated measures to account for within patient correlation over time.

All the liver biochemistries and proinflammatory cytokine profile over time will be analyzed using mixed model with repeated measures to investigate how VC treatment plays a role over the 6 months duration. The liver biochemistries and proinflammatory cytokine will be dichotomized into abnormal and normal groups if possible and further the abnormal proportions at different time points will be estimated to see the trend over time.

The incidence, type and relatedness of serious adverse events and adverse events will be monitored and reported for all the subjects.

Adherence to Regulatory Standards: The investigators will ensure that this study is conducted in full conformity with Regulations for the Protection of Human Subjects of Research codified in 45 CFR Part 46, 21 CFR Part 50, 21 CFR part 56, and the ICH; Good Clinical Practice E6.

ClinicalTrials.gov Requirements: The principal investigator will ensure that this clinical trial is properly registered at www.clinicaltrials.gov, per the Public Law 110-85 (also known as the FDA Amendments Act (FDAAA) of 2007), no later than 21 days after the first subject is enrolled. The principal investigator will also ensure that the results (including adverse events) of this clinical trial are reported no later than 1 year after completion of the clinical trial.

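### Aim 3 asks whether early cytokine changes predict ALP response, but no planned analysis relates the two across patients, and the one stated criterion can be met without any association

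*Combined protocol and SAP*

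**What the plan says.** The Specific Aims (Approach) state Aim 3 as "Determine if changes in the proinflammatory cytokines IL-17 and IFNy predict response to VC". Study Design and Methodology gives the week-4 sample its purpose: "The early 4-week time point will be used to determine whether early changes in these cytokines may predict improvements in ALP". Protection of Human Subjects, section I(a), repeats it: cytokine levels are compared with baseline "to determine whether early changes in these proinflammatory cytokines may predict improvements in ALP". Importance of the Knowledge to be Gained adds that the study will supply evidence on whether the two cytokines can serve as early markers of ALP improvement.

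Only one sentence says what result would count. In Study Design and Methodology, a week-4 reduction in both cytokines "concomitant with reduced ALP at the end of study would indicate a role for cytokine levels as an early predictor of improvements". It names no test, threshold or comparison group.

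The Statistical Analysis Plan has two statements on cytokines: "All the liver biochemistries and proinflammatory cytokine profile over time will be analyzed using mixed model with repeated measures", and, after dichotomising where possible, "the abnormal proportions at different time points will be estimated to see the trend over time". ALP gets an exact binomial interval for normalization and its own mixed model. The within-patient correlation mentioned there concerns repeated ALP values, not cytokine with ALP.

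**The concern.** Prediction is a statement about differences between patients: those whose cytokines fall more at week 4 should be those whose ALP falls more by month 6. Two markers falling together on average does not show this.

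The protocol's own hypotheses make a joint fall likely for another reason. Expected Outcome says "daily treatment with vidofludimus calcium will result in reduction of serum ALP" and also "we hypothesize that treatment will result in a decrease in certain proinflammatory cytokines". A drug that acts on each marker separately would satisfy the criterion. Regression to the mean could also contribute, because entry requires ALP of at least 1.5 times the upper limit of normal and there is no control arm.

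Reading the criterion patient by patient does not rescue it. Counting patients in whom everything fell still omits the comparison with patients whose cytokines did not fall.

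At stake is a claim that these cytokines are early markers, carried forward into the design of later studies. No dosing, stopping or success decision depends on it.

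**Working it through.** The documents give no effect size, SD, correlation or alpha for Aim 3, so there is no figure of theirs to reproduce. What follows is an illustration.

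**Inputs from the documents.** Single arm, 30 patients (Study Design and Methodology), as few as 20 allowed (Risk Mitigation and Alternative Strategies). Cytokines at baseline, week 4 and month 6 (Timeline and Schedule).

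**Assumptions.** Normal change scores for IL-17, IFN-gamma and ALP; equal mean falls of 0.3, 0.5 or 0.8 SD; cytokine–cytokine correlation 0.5; complete pairs. Two cases: cytokine–ALP correlation 0, or 0.6 for each cytokine.

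**Step 1: group reading, means only.** A mean of n changes with fall d SD lies below zero with probability Φ(d√n). For n=30, d=0.5 this is Φ(2.74)=0.997 per marker. Jointly, by simulation, all three means are lower in 99% of trials at correlation 0 and 99% at 0.6. For d=0.3: 87% v 89%.

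**Step 2: group reading, each fall significant** (one-sample t-test, two-sided 5%). Share of trials with all three significant, correlation 0 v 0.6:

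| Mean fall | n=30 | n=20 |
|---|---|---|
| 0.3 SD | 7% v 15% | 3% v 8% |
| 0.5 SD | 47% v 56% | 22% v 32% |
| 0.8 SD | 97% v 97% | 80% v 83% |

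The result is driven mainly by the size of the mean falls. A simpler version with one cytokine and ALP, correlation 0 v 0.5, agrees: at n=30 and 0.5 SD, both means are lower in 99% v 99% and both falls significant in 56% v 62%.

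**Step 3: patient-by-patient reading.** With no mean change and correlation 0, both cytokines fall in 1/4 + arcsin(0.5)/(2π) = 1/3 of patients and ALP in 1/2, so 30 × 1/3 × 1/2 = 5 patients show all three falls by chance; with correlation 0.6 about 8 do. At 0.5 SD the counts are about 11 v 14 of 30. A count alone therefore mixes mean effect with association.

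**Step 4: the omitted comparison.** At 0.5 SD, ALP falls in Φ(0.5)=69% of patients overall.
- Correlation 0: 69% of patients whose two cytokines fell, 69% of the rest.
- Correlation 0.6: 87% and 47%.

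**Step 5: a direct association test.** Spearman, two-sided 2.5% per cytokine: positive in about 2.5% of trials at correlation 0, and at 0.6 in 88% (n=30) or 67% (n=20). Mean falls do not affect it, since a constant shift leaves ranks unchanged.

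**Step 6: what that test can detect.** At 80% power, r = tanh[(2.241 + 0.842)/√(n−3−k)], with k baseline covariates.
- Pearson, k=0: tanh(3.083/√27)=0.53 (n=30); tanh(3.083/√17)=0.63 (n=20).
- Adjusted, k=2: tanh(3.083/√25)=0.55; tanh(3.083/√15)=0.66.
- Spearman (variance × 1.06): 0.54 and 0.65.

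**The case against.** The strongest reply is about weight. This is the third aim of an openly exploratory pilot, the language is hedged, and the paired samples will exist, so the association could be computed later. The protocol does commit to examining prediction; on this view it lacks a method rather than planning a bad one, and simulating a narrative sentence as a decision rule makes it look firmer than it is. This stands as a reason to rate the point as moderate. It does not remove it: the sentence still says what finding would be taken as prediction, and choosing the method after seeing 20 to 30 patients leaves method and time point open.

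The illustration also depends on assumptions. Requiring significance, the criterion's rate roughly doubles under true association at 0.3 SD (7% to 15%), so it is not wholly insensitive. A 25% threshold for reduced ALP, which the same section uses elsewhere, was not simulated. A correlation of 0.6 flatters the remedy: at 0.3, 0.4 and 0.5 the Spearman test is positive in about 24%, just over 40% and just under 70% of trials at n=30, and about 15%, 27% and 45% at n=20. Undetectable cytokine values would cost more: with 30% or 50% undetectable at baseline (assumed, with equal unit SDs for log baseline and log change and a 0.5 SD fall), the 88% drops to about 55% or 41%. These points stand. They limit what the added analysis can show, but they do not make the present criterion a test of prediction.

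Finally, response is not fixed for this aim: the design section uses a 25% ALP improvement with an AST limit, the Statistical Analysis Plan uses normalization, and the criterion says only reduced ALP. That is fair, and any added analysis must name its outcome.

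**Conclusion.** The concern holds. No listed analysis relates cytokine change to ALP change across patients, and the only stated criterion can be satisfied by two unrelated drug effects. That the analysis is absent, and that the criterion does not require association, follows from the text alone. The size rests on the assumed effect sizes and correlations above: at moderate to large mean falls the criterion separates association from no association poorly, while a direct correlation separates them well if the true correlation is strong. It should be corrected, but the primary analysis and the trial's conduct are unaffected.

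**What to change.** In Study Design and Methodology, replace the sentence containing the criterion with:

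> An association across patients between week-4 cytokine change and month-6 ALP change would support cytokines as a candidate early marker.

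In the Statistical Analysis Plan, add:

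> Exploratory: for each cytokine, the Spearman correlation between the week-4/baseline cytokine ratio and the month-6/baseline ALP ratio will be reported with a 97.5% CI, with the number of patients having both. Undetectable values will be set to the assay limit before ratios are formed, and their number reported. For this aim, response means the continuous ALP ratio. This single-arm trial cannot separate prediction of response to VC from general prognosis.

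If few values are undetectable, regression of the log ALP ratio on the log cytokine ratio, adjusted for baseline ALP and baseline cytokine, is an acceptable alternative and deals with baseline ALP directly. Any detectable correlation quoted should match the method chosen.

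The cost is one reworded sentence and one estimate per cytokine, with no new visit or assay. The price is imprecision. For an observed Pearson r of 0.3, tanh[0.3095 ± 2.241/√(n−3)] gives a 97.5% CI of about −0.12 to 0.63 at n=30 and −0.23 to 0.69 at n=20; Spearman intervals are slightly wider. The report should say so.

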These results will help us:

- Establish feasibility of the hypothesis that VC will play a therapeutic role in treatment of PSC
- Gain insight into the effect of VC on profiles of the proinflammatory cytokines IL-17 and IFNy
- Pave the way for more comprehensive clinical studies

Study Design and Methodology

This pilot study will be a 6-month, 30-subject clinical trial to assess the effects of VC on a surrogate biochemical endpoint known to have relevant association with clinical outcomes in PSC. All endpoint tests chosen are rapid, inexpensive, and minimally invasive. Due to the low prevalence of PSC, the study will be a single-arm, open-label study. The study will be undertaken at two sites, Mayo Clinic, Rochester, Minnesota (20 subjects) and Mayo Clinic, Phoenix, Arizona (10 subjects), both of which are tertiary referral centers for PSC. Immunic AG, a biotechnology company based in Munich, Germany, will supply the study agent in sufficient quantities for the study (see Letter of Support from Immunic AG). We have confirmed through consultation with NIH personnel that this is permissible under this funding opportunity.

During the 6-month treatment period, subjects will receive 30 mg VC orally once daily, a dose determined to be both safe and therapeutically relevant based on previous clinical studies (see Table 1). This will be preceded by a lead-in dosing period where subjects will receive 15 mg VC once daily for 1 week. Lead-in dosing is used to minimize the risk of drug intolerance during the initial treatment period. While no clinically relevant adverse events have been noted at 30 mg once daily dosing, in rare instances potentially drug-related hematuria has been observed in the first few days of treatment at higher doses (≥ 70 mg/day). As a precaution, subjects will be monitored for two weeks after initial drug

exposure for elevated erythrocytes in the urine by a dipstick test. It is not anticipated that hematuria will be seen if it has not developed within the first two weeks of drug exposure.

The following endpoints will be assessed at various times during the study and compared with baseline:

- i. Primary endpoint:
 - a. Improvement of serum alkaline phosphatase (ALP) [baseline, 3 months, and 6 months]
- ii. Secondary endpoints:
 - a. Bilirubin, Total and Direct [baseline, 3 months and 6months]
 - b. AST and ALT (aspartate and alanine transaminases) [baseline, 3 months, and 6 months]

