At the end of the 6-month treatment, any subjects demonstrating benefit may optionally continue VC treatment under a single-patient IND. Subjects without benefit will return to standard of care for PSC patients. All subjects will receive a post-study follow-up assessment at 30 days to capture any remaining adverse events.

Timeline and Schedule

For each subject, study participation will consist of a screening period of up to 1 month, a lead-in dosing period of 1 week, treatment period of 6 months, and a follow-up period of up to 1 month. A recruitment period of no more than 6 months is anticipated. Subjects will be seen in clinic at baseline and at the end of the treatment period, where safety, clinical and laboratory evaluations will be performed. Screening and Baseline Visits may be done on the same day. Any procedures done to meet inclusion/exclusion criteria at Screening do not need to be repeated for the Baseline values at the discretion of the investigator. Every other day during the first two weeks, urine dipstick testing for hematuria will be performed. Between the clinical visits, patients will have laboratory tests and be monitored by phone call every 4 weeks throughout the treatment period, and again at 1 month after completion of the treatment period for safety, adverse events, subject health, and adherence to the study protocol. Safety monitoring tests will include AST, ALT, ALP, TBIL, DBIL. Cytokines (IL-17 and IFN- γ) will be tested at Baseline, 4 weeks, and 6 months. Blood will be collected at Baseline, 4 weeks, 3 months, and 6 months and stored for potential future analysis. Images from the MRCP and results from the Fibroscan, both done as standard of care, will be recorded at Screening /Baseline and at 6 months. If images from the MRCP or results from the Fibroscan are not performed as standard of care or are not available from the medical record, they do not need to be performed for the study. Women of childbearing capability will undergo monthly pregnancy tests. It will be required that both patient and partner use a barrier method as well as hormonal contraception while on study. If patient or partner has had onset of menopause, a hysterectomy, tubal ligation, or vasectomy, no other contraception is required. Those with a confirmed positive test will be removed from the study.

Pharmacokinetic Sample

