Due to the relatively low prevalence, it is possible that 30 subjects meeting inclusion criteria cannot be recruited within the planned 6-month recruitment period or that they are not split roughly equally between the two sites. In that case, we will extend the recruitment period and if required, we will execute the study with as few as 20 subjects, regardless of the distribution between sites. After the study is complete, further research may reveal other potentially interesting biomarkers that should be examined and thus we have included storage of extra blood draws during the study. Given the pilot nature of this study, it is possible that benefits are seen even though results are not conclusive. Study data may be examined more carefully to determine if benefits occur in a distinct subpopulation of subjects (e.g. in PSC patients with UC versus those without).

Overall, considering the known safety data, the implemented risk minimization measures, the expected benefits in the target population, and the unmet medical need for treatment in PSC, the risk-benefit evaluation is considered favorable.

PROTECTION OF HUMAN SUBJECTS

This Human Subjects Research meets the definition of a clinical trial.

I. Risks to Human Subjects

a) Human Subjects Involvement, Characteristics, and Design: A total of 30 adults (age range 18-75 years) who meet the criteria for diagnosis of primary sclerosing cholangitis (PSC), as defined by the American Association for the Study of Liver Diseases (AASLD) published guidelines, will be enrolled into this study from two centers. PSC patients with and without inflammatory bowel disease (IBD) will be included. Other inclusion and exclusion criteria are detailed below:

Inclusion Criteria

- a. Male or female subject age 18-75 years
- b. Diagnosis of PSC consistent with the guidelines published by the AASLD. All subjects must have an elevated serum ALP of at least 1.5 times upper limit of normal (ULN) at baseline plus cholangiographic evidence of PSC (MRI, endoscopic retrograde cholangiography, or direct cholangiography).
- c. Indirect bilirubin <1.2 times the ULN
- d. An ultrasound (or equivalent imaging modality) that excludes biliary obstruction and malignancy within 6 months of study enrollment
- e. PSC with or without inflammatory bowel disease, such as ulcerative colitis or Crohn's disease
- f. Must agree to comply with the study protocol and provide informed consent

Exclusion Criteria

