Cytokine testing (IL-17 and IFN-γ)		x		x			x				x		

a Screening and Baseline Visits may be done on the same day. Any procedures done to meet inclusion/exclusion criteria at Screening do not need to be repeated for the Baseline values at the discretion of the investigator. **b** If not available from medical record, does not need to be performed for the study. **c** Study may be mailed to participant after Baseline Visit once all test results available. **d** Will be tested at screening if unavailable from medical record

c) Potential Risks:

1. Risks related to the study drug (VC)

Risks associated with the use of VC include hematuria early in the course of treatment. Although no clinically related adverse events were observed at doses of vidofludimus >70 mg, at higher doses potential drug-related increases in urine red blood cells (RBCs) and hematuria were observed. The underlying mechanism leading to increased red blood cells in urine appears to be increased uric acid elimination during the initial days after drug administration. Inhibition of the urate transport system URAT1 by VC may decrease the tubular re-uptake of uric acid in kidneys, leading to increased uric acid in the urine. This may in turn result in microcrystallization of uric acid in acidic urine and may lead to the occurrence of red blood cells in urine. Although this may not normally lead to clinically relevant adverse events at therapeutic doses, it may be important for patients with a risk factor of increased serum uric acid.

During clinical trials using vidofludimus, one serious adverse event of hepatitis was reported in a subject with Gilbert syndrome. Gilbert syndrome, which is associated with elevated blood levels of unconjugated bilirubin, is a genetic disease characterized by an up to 70–80% reduction in the glucuronidation activity of UGT1A1. The fact that VC is a moderate inhibitor of UGT1A1 may have contributed to this adverse event. Thus, patients with known or suspected Gilbert syndrome or with elevation of indirect (unconjugated) bilirubin above 1.2 time upper limit of normal (ULN) will be excluded from this clinical study.

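### ALP must be at least 1.5 × ULN at baseline and the same reading is the comparator, so regression to the mean modestly favours the drug in the ALP change analyses

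*Combined protocol and SAP*

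**What the plan says.** Inclusion Criteria, item b, sets the entry threshold on the baseline reading: "All subjects must have an elevated serum ALP of at least 1.5 times upper limit of normal (ULN) at baseline".

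The same reading is the reference for change:

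- Specific Aims, Aim 1: "Levels of serum ALP after 3 and 6 months of VC treatment will be compared with baseline (month 0".
- Study Design and Methodology introduces its endpoints with "The following endpoints will be assessed at various times during the study and compared with baseline" and gives the primary endpoint as "Improvement of serum alkaline phosphatase (ALP) [baseline, 3 months, and 6 months".
- The same section, and Protection of Human Subjects, count as a positive outcome "A 25% improvement in ALP with no more than a 33% worsening of AST after 6 months of treatment".
- The Statistical Analysis Plan adds a repeated-measures mixed model asking whether absolute ALP goes down over time.

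Timeline and Schedule lets Screening and Baseline fall on one day and adds: "Any procedures done to meet inclusion/exclusion criteria at Screening do not need to be repeated for the Baseline values". Table 3, footnote a, repeats the allowance. As extracted, Table 3 (whose layout is partly broken) lists ALP from Baseline and not at Screening.

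The Statistical Analysis Plan names a different primary endpoint, the ALP normalization rate at 6 months, with success if the exact 95% interval excludes 0. There is no control arm. No section mentions regression to the mean, or a confirmatory, averaged or separate baseline reading.

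**The concern.** A lower cut-off on a variable measured with error preferentially admits patients whose error on that day was positive. The error is not carried forward in full, so later readings are lower on average even if the drug does nothing. In a randomized trial the control arm would show the same fall and cancel it. Here nothing does, and the artefact has the same sign as benefit.

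The change analyses matter even though the SAP defines success by normalization. Study Design and Methodology says "full normalization of ALP levels is unlikely over the short course of this pilot study" and treats a 25% fall as the positive result. Evidence of activity, and the case for a larger trial, is therefore likely to be read from ALP change. If no ungated pre-dose ALP is collected, the bias cannot be repaired after the trial.

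**Working it through.** The plan gives no ALP variability, no sample-size calculation and no figure for regression to the mean, so there is no stated number to reproduce.

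**Inputs from the documents:** threshold 1.5 × ULN at baseline; n = 30 planned, 20 at minimum; ALP every 4 weeks to week 24; one arm.

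**Assumptions (not in the documents):** log-normal true ALP with median 1.8 or 2.5 × ULN before selection and between-patient log-SD (sb) 0.4 or 0.6; independent log-normal visit error (sw) of 0.20, varied from 0.10 to 0.30; no drug effect.

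**Formula.** With st² = sb² + sw² and z = ln(1.5/median)/st, the expected log change from a gated baseline is −(sw²/st) × φ(z)/(1 − Φ(z)).

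**Example (median 1.8, sb 0.4, sw 0.20).** st = √(0.16 + 0.04) = 0.447. z = ln(1.5/1.8)/0.447 = −0.408. φ(z)/(1 − Φ(z)) = 0.367/0.658 = 0.558. Change = −(0.04/0.447) × 0.558 = −0.050, a geometric-mean fall of 4.9%.

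**False falls.** The SAP does not specify a test of change. A one-sample t on month 6 minus baseline stands in for the mixed model. A false fall is counted when the two-sided 95% interval lies wholly below 0 (nominal 2.5%). Simulated results at sw = 0.20, n = 30:

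| Median, sb | Geometric-mean fall | Mean absolute fall | False falls, absolute | False falls, log | False falls, absolute, ungated day-0 baseline | Share with ≥25% fall |
|---|---|---|---|---|---|---|
| 1.8, 0.4 | 4.9% | 3.3% | 9.6% | 16.2% | 2.4% | 19.4% |
| 1.8, 0.6 | 3.9% | 2.1% | 6.2% | 11.6% | 2.3% | 18.7% |
| 2.5, 0.4 | 2.1% | 1.2% | 4.0% | 6.0% | 2.4% | 16.9% |
| 2.5, 0.6 | 2.3% | 1.1% | 3.8% | 6.4% | 2.3% | 17.2% |

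Without selection on the comparator, the share with a 25% fall from noise alone is Φ(ln 0.75/(0.20 × √2)) = Φ(−1.017) = 15.5%.

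**Sensitivity:**

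- n = 20, month 6: false falls of about 3–8% on absolute ALP.
- Linear trend over weeks 0–24, n = 30: 3–7% absolute, 5–11% log.
- sw from 0.10 to 0.30, n = 30: 3–15% absolute. At 0.30 the geometric fall is 5–10%.
- Pre-selection median as low as 1.5 × ULN and within-patient CV of 10–30%: geometric fall 0.5–12.9%, false falls on a log-scale test 4–47%.
- Sites already gating on both an earlier and a day-0 ALP: 1.4–3.2% geometric fall, 3–6% false falls (absolute).

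**Normalization.** No baseline value enters this endpoint, but admitting patients on one noisy reading raises the drug-free chance of at least one month-6 normalizer among 30. At sw = 0.20 it is 7–24% with one gate, against 3–7% if entry were on true ALP. One normalizer meets the success rule, since the exact lower limit for 1/30 is 1 − 0.975^(1/30) = 0.08%.

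**The case against.** The strongest reply has four parts.

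1. **The formal success rule uses no baseline value.** This stands: the point is confined to the change analyses, and its fix does not cure drug-free normalization.

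2. **The plan sets no significance test on ALP change.** The false-fall rates therefore describe a decision it does not formally make, and the log-scale rates are not on the SAP's absolute scale. This is fair, and is why the absolute figures lead here. But the SAP does ask whether ALP falls over time, and a reader will judge that by an interval or p-value. Against the 25% criterion the effect is small: 17–19% reach it instead of about 15%.

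3. **The size is wholly assumed.** True. Wider assumptions give a larger bias and smaller within-patient error a smaller one. The sign does not change.

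4. **The repair is imperfect.** If errors on the qualifying and day-0 readings correlate at 0.5, a geometric fall of 1.1–2.5% and false falls of 3–5% (absolute) remain. An ungated day 0 also admits some patients below the threshold that day. Both are real costs.

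The no-repeat allowance is also thin support, because Table 3 seems to draw ALP only from Baseline. The case rests on criterion b itself: if the only pre-dose ALP is the baseline draw, that draw is both gate and comparator. That the study is a small pilot argues for a modest grade, but a limitation statement alone would leave the data biased when the bias can be avoided at low cost.

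**Conclusion.** The point holds. As written, the reading that admits patients is also the comparator for ALP change, no control arm absorbs the resulting fall, and the bias favours the drug. Under the central assumptions (median 1.8–2.5 × ULN, between-patient log-SD 0.4–0.6, within-patient log-SD 0.20, independent errors, n = 30) it is a 1–3% spurious fall in mean ALP and roughly a 1.5- to 4-fold rise in false falls on the absolute scale. That is modest next to 25%, and it does not bias the normalization endpoint through its comparator. It should be changed because it is avoidable and cannot be corrected later. Confidence in the direction is high. Confidence in the size is medium, because the documents supply none of the variability inputs.

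**What to change.** - **Inclusion Criteria b:** apply the 1.5 × ULN threshold to a qualifying ALP from an earlier date (chart or screening), within a window the sponsor sets.
- **Timeline and Schedule, and Table 3 footnote a:** exempt ALP from the allowance that results "do not need to be repeated for the Baseline values at the discretion of the investigator".
- **Statistical Analysis Plan:** define baseline ALP, for every ALP change analysis, as a separate pre-dose day-0 value to which the threshold is not applied.

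With independent errors this returns false falls to 2–3%.

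**Cost.** One routine ALP assay on blood already drawn at baseline, plus an earlier draw for patients with no prior ALP, for example when Screening and Baseline share a day. About 6–14% of patients (3–20% over within-patient log-SD 0.10–0.30) would have a day-0 ALP below 1.5 × ULN.

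**If sites would otherwise gate on both an earlier and a day-0 ALP,** dropping the day-0 gate raises the drug-free chance of at least one normalizer from 3–8% to 7–24%. The sponsor can avoid this by placing both gates before day 0 and leaving day 0 ungated. That keeps the chance at 3–8% with false falls at 2–3%, for one more earlier ALP.

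**Optional supporting check:** the ALP trend from week 4 to week 24. It is free of the artefact only if visit errors are independent, and it cannot show an effect already complete by week 4.
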